3. STUDY DESIGN ASPECTS

We consider sending Participant Information Sheet (PIS) about the present study to patients due to have colonoscopy via regular mail along with their appointment letter. Research Nurses are already available on both sides will inform and consent patients for blood sampling. We consider let all participants know about the analysis of results of this study. A letter will be

sent with the main findings and the potential implications for the future of the bowel cancer screening.

Blood sample will be Centrifuged and serum will be kept frozen at -80°C in both hospital sites until it will be transferred to the Biomedical and Life Sciences, Lancaster University for ELISA measurement.

Each Participant will be explained the objectives of the study, will sign the consent form for participation and will be cannulated for colonoscopy (the vast majority of patients undergoing colonoscopy wish to have sedation/analgesia) and blood will be drawn from the cannula before the administration of the sedation/analgesia for their colonoscopy.

Two of the investigators ([name] and [name] will be involved in participants colonoscopy.

Participant data or samples will be identified by the unique study number. Participants will not be referred to a separate research team and the arrangements for identification and referral will be kept strictly to the participating trusts. The aforementioned information will be explained clearly in the letter of invitation and/ or written information for participants. In the occasional case that we will recruit prisoners, their GP will receive all the necessary information.

The initial approach to potential participants should be made by a member of the healthcare team responsible for patients' colonoscopy as it is normally done in the endoscopy unit. The research Nurse will be present as well in order to inform and consent patient for the taking of the blood sample. The identification of potential participants will not involve reviewing or screening the identifiable personal information. Research will entail the taking

participant blood, measurement of biomarkers and statistical analysis to document their predictive value. There will not be any direct or indirect clinical implication to participant health care management.

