3.3 OUTCOME MEASURES

The primary endpoints are firstly the cut-off of the serum Neurotensin and IL-8 values selected by the ROC curves and the demonstrated estimate of area under ROC curve (accuracy) in predicting colorectal cancer and colorectal adenomas.

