3.5 PROPOSED SAMPLE SIZE / POWER CALCULATIONS

Assuming that the AUC of the new test is commensurate with the pilot study (AUC=0.85), we calculate the number of samples required to obtain a 95%

confidence interval of size 0.1. We assume that the ROC curve follows a binormal distribution, and that the prevalence of adenoma/cancer is between 20-30% in the study participants. We obtain that we require between 400 (30% prevalence) and 553 (20% prevalence) participants. We therefore target an enrollment of 500 patients. We intend to perform an interim analysis after 50% of the patients have been included and evaluated.

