3.6 FEASIBILITY OF RECRUITMENT

The collaborative departments (Surgical Department and Gastroenterology department) of Royal Preston Hospital and the respective departments from Furness General Hospital screen approximately 18-20 cases per week. Assuming a participation rate of 50%, 500 patients can be recruited during a 12 months' period.

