4. STATISTICAL ANALYSIS

4.1 Confirmatory analysis of primary endpoints

In order to compare the low to high risk groups, the propensity score will be used that is the probability of a case being in a particular group based on a given set of covariates (e.g., age, gender, BMI and ethnic background). Generally, will be calculated using logistic regression with group (Treatment /Control) as dependent and covariates as independent variables. In order to deal with missing data in covariates, we will apply multiple imputation by either Separate creation of propensity scores from the matching or we will aggregate cases to get mean (median) propensity score. H0: p1=p2 is tested against the alternative H1: $p1 \neq p2$ using the exact Fisher tests.

A receiver operating characteristic (ROC) curve will be used to summarize the performance of the two-class classifiers (for Neurotensin and IL-8) for cancer and adenomas across the range of possible thresholds.

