4.5 Interim analysis

An interim analysis with regard to the primary endpoint will be performed after inclusion and evaluation of 250 persons. If H0 can be rejected at this stage the study will be stopped. All persons included in the study up to the decision to stop will be evaluated and considered for a secondary analysis. If H0 cannot be rejected at this stage, a re-design is possible because of the adaptive strategy.

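### After an early stop, section 4.5 calls the analysis of everyone included secondary, which implies that the primary AUC and cut-offs come from the 250 interim participants, the less precise set

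*Protocol*

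**What the plan says.** Protocol section 4.5 sets the timing: "An interim analysis with regard to the primary endpoint will be performed after inclusion and evaluation of 250 persons". The rule follows: "If H0 can be rejected at this stage the study will be stopped". The next sentence is the only one in the protocol that gives the data a role after such a stop: "All persons included in the study up to the decision to stop will be evaluated and considered for a secondary analysis".

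Other sections that bear on it:

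- Section 3.3 makes the primary endpoints estimates: "The primary endpoints are firstly the cut-off of the serum Neurotensin and IL-8 values selected by the ROC curves", together with the area under the ROC curve.
- Section 3.5 sizes the study only on a 95% confidence interval of size 0.1 around an AUC of 0.85.
- Section 3.6 gives the recruitment rate: 18 to 20 cases per week are screened, and "Assuming a participation rate of 50%, 500 patients can be recruited during a 12 months' period".
- Section 3 describes the sample path: "serum will be kept frozen at -80°C in both hospital sites until it will be transferred to the Biomedical and Life Sciences, Lancaster University for" assay there. Section 3.1 assigns groups only after the colonoscopy and histology reports.

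**The concern.** Between the 250th participant's blood sample and a decision to stop, samples must be moved to the university and assayed, histology must be reported, and the interim must be analysed. The protocol mentions no pause in recruitment, and section 4.5 itself provides for people included up to the decision. Some further participants are therefore likely to be enrolled.

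Those later participants enter under the same criteria and have the same index test and reference standard as the first 250. The protocol gives no reason to rank the analysis that contains them below the one that does not. For an endpoint that is an estimate, and a study sized on the precision of that estimate, the headline figure should come from the largest valid set. The label in section 4.5 implies the reverse: a wider interval is primary and a narrower one, from data already in hand, is secondary. The cut-offs carried forward to a later study would come from the smaller set too.

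**Working it through.** **Inputs from the protocol.** AUC 0.85, binormal ROC curve, 95% confidence, full interval width 0.1, adenoma/cancer prevalence 20% to 30% (section 3.5); interim at 250 (section 4.5); 18 to 20 cases per week at 50% participation (section 3.6).

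**Assumption.** The lag from the 250th participant to the decision is not given. A range of 2 to 12 weeks is used.

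**1. Reproduce the protocol's sample size.** The usual binormal variance is

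V = 0.0099 × exp(−A²/2) × [(5A² + 8) + (A² + 8)/k],

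with A = 1.414 × z(0.85) and k = controls per case. Then cases = 1.96² × V / 0.05², and N = cases / prevalence.

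- A = 1.414 × 1.036 = 1.465, so A² = 2.148.
- Prevalence 30%, k = 0.7/0.3: 120.0 cases, N = 400.0. The protocol has 400.
- Prevalence 20%, k = 4: 110.6 cases, N = 552.9. The protocol has 553.

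Both figures reproduce, so this is a fair basis for what follows.

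**2. Size of the overrun.** Enrolment is 18 × 0.5 = 9 to 20 × 0.5 = 10 per week. The overrun is 9 × 2 = 18 to 10 × 12 = 120 people, for a total of 268 to 370.

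**3. Interval width by analysis set.** Width = 2 × 1.96 × √(V / cases), which equals 0.1 × √(N from step 1 / N analysed).

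| N analysed | Width at 20% prevalence | Width at 30% prevalence |
|---|---|---|
| 250 (interim set) | 0.149 | 0.126 |
| 268 (2 weeks at 9) | 0.144 | 0.122 |
| 370 (12 weeks at 10) | 0.122 | 0.104 |
| 500 (no early stop) | 0.105 | 0.089 |

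From unrounded widths, using everyone narrows the interval by 0.004 to 0.005 at the short lag and by 0.023 to 0.026 at the long one. In relative terms the ratios are √(250/268) = 0.966 and √(250/370) = 0.822, so the interval is about 3% to 18% narrower. No set up to 370 reaches 0.1.

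**4. Does stopping bias the estimate from the 250?** A simulation of 250 participants (4,000 runs per setting) took H0 as AUC = 0.5, tested at two-sided 0.05. Both are assumptions: section 4.1 states only "H0: p1=p2 is tested against the alternative" of unequal proportions, and section 4.5 gives no boundary.

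| True AUC | Chance of stopping (prevalence 20%; 30%) | Mean AUC given a stop (20%; 30%) |
|---|---|---|
| 0.85 | about 100%; about 100% | 0.85; 0.85 |
| 0.60 | 60%; 71% | 0.63; 0.62 |
| 0.55 | 19%; 24% | 0.61; 0.60 |

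At the planning value there is no inflation. It appears only for a weak marker. Pooling would dilute it: at a true AUC of 0.60 and 20% prevalence, adding 120 unselected participants gives roughly (250 × 0.628 + 120 × 0.600)/370 = 0.619, weighting simply by sample size.

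**The case against.** Four objections have force.

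- **The text discards nobody.** A reader might infer that people enrolled after the 250th are thrown away or go only to a secondary analysis. The sentence does not say so. It covers all persons, the first 250 included, and says that they will be evaluated. The contrast is between a 250-only result, primary by implication, and an all-participant result labelled secondary.
- **Separating the decision from the overrun is accepted practice.** Resting the stopping decision on the planned interim set and reporting everyone in a further analysis is a recognised way to handle overrunning. That protects the decision. It does not require the reported estimate of an AUC to come from the smaller set.
- **The estimation set could be left to the analysis plan.** This would answer the point if the protocol were silent. It is not: it assigns a label, and an analysis plan that follows it would inherit the ordering.
- **The numbers are soft and the gain is small.** The lag is assumed. The widths pool adenoma and cancer as section 3.5 does, whereas section 3.1 has two primary comparisons, each against normal colonoscopy, so neither primary AUC has exactly these widths. The relative narrowing in step 3 carries over if the case mix is stable. Most of the lost precision comes from stopping near 250 at all.

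A reader might also infer that the headline AUC would be badly inflated because it triggered the stop. Step 4 does not support that at the planned AUC of 0.85. Nor would the change remove selection, since the same 250 stay in the estimate.

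**Conclusion.** The point holds in a limited form. Section 4.5 ranks the all-participant analysis as secondary after an early stop, and so implies that the primary AUC and cut-offs are those on 250. For an endpoint sized on interval width, that is needlessly imprecise: 0.149 to 0.126 wide on 250, against 0.144 to 0.122 with 18 more participants and 0.122 to 0.104 with 120 more. The target of 0.1 is missed either way. The figures rest on the protocol's binormal model at AUC 0.85, pooled prevalence of 20% to 30%, section 3.6 recruitment, and an assumed lag of 2 to 12 weeks. Selection from stopping is negligible near AUC 0.85 and matters only for a weak marker. This is a cheap improvement, not a threat to the study's validity.

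**What to change.** Replace the sentence in section 4.5 with:

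> The decision to stop uses the 250 interim participants. If recruitment is stopped, the primary reported AUC with 95% CI and the cut-offs will be estimated from all evaluable participants included up to the stop, with the estimate on the first 250 shown alongside as the interim result.

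Settle this before the interim result is seen. It changes one sentence and needs no extra patients or assays, because these participants are to be evaluated already. The downside is that the final AUC may be slightly less favourable than the interim value; showing both keeps that visible.

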5. ETHICAL CONSIDERATIONS

5.1 Consent

We strongly support the concept that for participants to be enrolled in the study will have the capacity to decide for themselves. The present research study will not involve participants who are unable to represent their own interests or are particularly susceptible to coercion. The aforementioned information will be highlighted to the research Nurses that they are going to consent patients for taking the blood samples. During the consent process participants will clearly be explained the purpose and nature of the research, its potential benefits or no benefits and risks and their right to withdraw consent at any time. We will make it clear that It is up to them to decide whether or not to take part. If they agree, will be asked to sign a consent form. Participants will be free to withdraw at any time without giving a reason. It will be clearly communicated that a decision to withdraw at any time, or a decision not to take part, will not affect the care they will receive.

5.2 Confidentiality

All participants will be reassured for keeping confidentiality according to the "Caldicott Principles" set out an ethical framework for use of identifiable data. Participant's data will be inserted and analysed under the hospital identification Number or NHS number.

Participants will be reassured that any information about themselves that leaves the hospital will have their name and address removed so that they cannot be recognised.

However, GPs may be informed of their participation in this study, but they may indicate their choice on the consent form.

If any problems arising from the processing of identifiable data and/or samples we will immediately let them know for a shared decision. Confidentiality to be broken if participants or others are at serious risk on rare occasions.

5.3 Risks, burdens and benefits

The procedure of drawing blood will be discussed with potential participants. The risks involved in drawing blood from a vein may include, but are not limited to, momentary discomfort at the site of the blood draw, possible bruising, redness, and swelling around the site, bleeding at the site, feeling of light-headedness when the blood is drawn, and rarely, an infection at the site of the blood. All participants will be reassured that drawing blood is a common daily hospital procedure entailing minimal risks and that all the necessary measures for dealing with side-effects are in place in the endoscopy setting (IV fluids, monitoring, and medications).

5.4 Conflict of interest

There are no conflicts of interests as a researcher which could potentially conflict with my duties as a health care professional.

5.5 What will happen at the end of our study?

After our study has ended and If the outcomes of our study are promising for detecting colorectal adenomas and cancer, an effort will be to conduct a multicentre study. The results will be fed back to participants according to their wish.

5.6 Use of tissue samples in future research

At the end of the study any surplus serum from your sample can either be gifted for use in other, different, research projects, subject to ethical approval, or disposed of as clinical waste in accordance with the relevant material of the Human Tissue Act 2004.

6.2 TRIAL-SUPPORTING FACILITIES

Two Research Nurses at both FGH and LTHTR sites: Will obtain patient consent responsible for blood sample collection and transfer to pathology laboratory for process and storing.

7. FINANCIAL SUMMARY

Item	Total funding period 12 months (£)	Costs
Kits for Neurotensin, IL-8	6 x human neurotensin ELISA	
	(CSB-E09144h): 2BScientific, 6 x	
	ELISA (enough for 488 samples,	
	allowing for optimization, £ 490	
	each=	Total cost:
	£ 2,940), quote # O-VM-18091101,	£ 4,000
	Cusabio	
	IL-8 from Peprotech	
	https://www.peprotech.com/human-	
	il-8-standard-tmb-elisa-	

	Cusabio offers at £ 520	
One-year Masters by F	Fees are £ 4,260 per annum	Total cost:
research student		£ 4,260
Case payment	• The total costs for processing 200	
(centrifugation at 3000 rpm	blood samples and storage at -20	
for 10 mins, and store at -	or -80 is £3,573	
20°C / -80 °C until assayed.		
ELISA measurements.	Additional lab costs amounting to	Total cost:
	£1500	
		£ 9,600
Research Nurses at both T	Top scale band 5 nurse x 0.25 FTE	
FGH and LTHTR sites. =	=18,395 x 0.25 x2	
Biostatistics S	Statistical consultancy rates range from	
£	285 to £120 UK pounds per hour.	Total cost: from
F	For a total of 20 hours from £ 1700 to £	£ 1,700 £ to
2	2400	£ 2,400
		~ 2,700
Charges for shipping,		Total cost: £ 200
delivery		101a1 COSI: £ 200

8. References

2 Screening for colorectal cancer: U.S. Preventive services task force recommendation statement. Ann Intern Med 2008;149:627-637.

3 Knudsen AB, Hur C, Gazelle GS, Schrag D, McFarland EG, Kuntz KM: Rescreening of persons with a negative colonoscopy result: Results from a microsimulation model. Ann Intern Med;157:611-620.

4 Hassan C, Giorgi Rossi P, Camilloni L, Rex DK, Jimenez-Cendales B, Ferroni E, Borgia P, Zullo A, Guasticchi G: Meta-analysis: Adherence to colorectal cancer screening and the detection rate for advanced neoplasia, according to the type of screening test. Aliment Pharmacol Ther;36:929-940.

5 National Comprehensive Cancer Network, Colorectal cancer screening (Version
2.2013), Accessed 16/12/2013,

http://www.nccn.org/professionals/physician_gls/gl_steering_committee.asp:

